7.5 Immunological Response

INCB024360 Cohorts:

70 mL of blood for immunological analysis (humoral and cellular immunity) will be collected via venipuncture using 6 green top and 1 red top collection tube. Sample collection will be obtained at the following visits:

- Cycle 1 Day 1
- Cycle 2 Day 1
- Cycle 3 Day 1
- Cycle 4 Day 1
- Cycle 5 Day 1
- Treatment discontinuation
- 3 Months, 6 Months, and 12 Months After Last Vaccine or last dose of INCB

Assays of samples to determine immune responses will be performed in the Immune Analysis Facility at the Center for Immunotherapy at Roswell Park.

Network Site see Appendix H for specific instruction.

Note: All investigator or analyzing research laboratories housing research samples need to maintain current Temperature Logs and study-specific Sample Tracking and Shipping Logs. The Principal Investigator/Laboratory Manager must ensure that the stated lab(s) have a process in place to document the receipt/processing/storage/shipping of study-related samples/specimens. This is required for both observational and interventional clinical studies collecting clinical samples.

Sirolimus Cohorts:

Blood samples will be collected via venipuncture for antibody response and cellular (T cell) immune response using ELISA for NY-ESO-1 and ELISPOT/ ICS (intracellular staining) respectively. Samples (70 ml) will be collected using 6 green top and 1 red top collection tube.

These samples for immunological analyses will be collected at the following visits:

- Cycle 1 Day 1
- Cycle 2 Day 1
- Cycle 3 Day 1
- Cycle 4 Day 1
- Cycle 5 Day 1

- Treatment discontinuation
- 3 Months, 6 Months, and 12 Months After Last Vaccine or last dose of sirolimus.

Samples will be kept at room temperature prior to processing. All samples to be sent to Immune Analysis Facility at Center for Immunotherapy:

Director: [name]

CCC building, 4th floor

[contact]

[contact]

Note: All laboratories housing research samples need to maintain current, study-specific **Temperature Logs** and **Sample Tracking and Shipping Logs**. The Principal Investigator/Laboratory Manager **must** ensure that the stated lab(s) have a process in place to document the receipt/processing/storage/shipping of study-related samples/specimens. This is required for both observational and interventional clinical studies collecting clinical samples.

7.5.1 Humoral Immunity

Specific antibody against NY-ESO-1 will be measured by ELISA (see Reference [7] for methodology).

7.5.2 Cellular Immunity

NY-ESO-1 specific CD4+ and CD8+ T cells will be measured by IFN γ release ELISPOT and Intracellular Cytokine Staining (ICS). Peripheral blood frequency of CD4+ CD25+ FOXP3+ regulatory T cells. Assays will be performed at the Immune Analysis Facility at the Center for Immunotherapy, Roswell Park, Buffalo, NY [42-44] for methodology). In order identify the DEC205mAb-NY-ESO-1 fusion protein with adjuvant poly-ICLC vaccination plus INCB024360 (or sirolimus for exploratory cohort) schedule that is associated with optimal biological activity, the following parameters will be determined (i) generation of effector and memory T cells with (ii) high avidity that are also (iii) resistant to T_{regs}.

7.6 Additional Exploration of the T cell response

The methods to analyze the T cell response to cancer antigens used in this study are well established. However, as T cell biology and immune regulation are very active fields of discovery, the opportunity exists to refine and extend the analysis of the T cell response. Therefore, although most of the blood drawn for the analysis of the immune response will be used for the assays listed above, a small part may be used to explore other aspects of the T cell response. In this regard, we will examine the evolution of memory CD8+ cells in the different patient cohorts. Using multi-parameter flow cytometry we will determine CD8+ cell subsets as follows: (i) central memory CD45RA-CCR7+CD27+ cells, which have the ability to migrate to lymph nodes; (ii) early and intermediate effector memory CD45RA-CCR7-CD27+ cells, with high proliferative capacity and low cytolytic activity; (iii) CD45RA-CCR7-CD27- cells, so-called late effector memory cells, with strong effector functions such as cytolytic capacity; and (iv) CD45RA+CCR7-CD27- cells, known

as fully differentiated effector cells, which retain those functional capacities but are stably non-replicative and apoptosis-resistant memory cells. On the basis of the distinct phenotypes of effector and memory CD8⁺ T cells generated by DEC205mAb-NY-ESO-1 fusion protein with adjuvant poly-ICLC vaccine in the presence or absence of IDO inhibition, we will determine whether the transition from an effector to a memory cell phenotype is an abrupt or gradual event, and whether this transition would occur simultaneously for different markers at the primary and secondary responses. This work may also involve establishing T cell lines and clones in culture, and collaborations with Investigators outside of Roswell Park.

7.7 Pharmacokinetic/Pharmacodynamic Blood Sample Collection and Processing

7.7.1 INCB024360 Levels

Whole blood samples for pharmacokinetic analysis of INCB024360 levels will be collected via venipuncture using (1) 4 mL purple-top EDTA collection tube per time point.

INCB024360 pharmacokinetic sample collection will be obtained on:

- Cohort -2, Cohort -1, and Cohort 1
 - Cycle 1 Day 1 and Day 15: predose and 1, 2, 4, and 6 hours post dose of INCB024360
 - Cycle 2 Day 1: trough, prior to vaccination
- Cohorts 2b
 - Cycle 1 Day 15: predose and 2 hours post dose of INCB024360
 - Cycle 2 Day 1: trough, prior to vaccination

Plasma will be separated by centrifugation at 4°C from whole blood within 30 minutes following the extraction and aliquotted into (2) cryovials per time-point.

Network Site see Appendix H for specific instruction.

Note: All investigator or analyzing research laboratories housing research samples need to maintain current Temperature Logs and study-specific Sample Tracking and Shipping Logs. The Principal Investigator/Laboratory Manager must ensure that the stated lab(s) have a process in place to document the receipt/processing/storage/shipping of study-related samples/specimens. This is required for both observational and interventional clinical studies collecting clinical samples.

Tryptophan and Kynurenone Levels:

Whole blood samples for pharmacokinetic analysis of tryptophan and kynurenone levels will be collected via venipuncture using (1) 4 mL purple-top EDTA collection tube per time point.

Tryptophan and kynurenone pharmacokinetic sample collection will be obtained on:

- Cohort -2, Cohort -1, and Cohort 1
 - Cycle 1 Day 1 and Day 15: predose, 1, 2, 4, and 6 hours post dose of INCB024360

- Cycle 2 Day 1: trough, prior to vaccination
- Cohorts 2b
 - Cycle 1 Day 15: predose and 2 hours post dose of INCB024360
 - Cycle 2 Day 1: trough, prior to vaccination

Plasma will be separated by centrifugation at 4°C from whole blood within 30 minutes following the extraction and aliquotted into (2) cryovials per time-point.

Network Site see Appendix H for specific instruction.

Note: All investigator or analyzing research laboratories housing research samples need to maintain current Temperature Logs and study-specific Sample Tracking and Shipping Logs. The Principal Investigator/Laboratory Manager must ensure that the stated lab(s) have a process in place to document the receipt/processing/storage/shipping of study-related samples/specimens. This is required for both observational and interventional clinical studies collecting clinical samples.

Sample Processing:

The screw cap polypropylene cryogenic tube will be labeled with the participant's MR number(for Roswell Park participants), patient's initials, patient's study number, clinical study number, protocol time point, dose, and protocol day. The label for each patient's sample will be supplied by Roswell Park. The samples will be immediately frozen at - 70°C or below until analyzed at the Roswell Park's Bioanalytics, Metabolomics & Pharmacokinetics Core Facility:

Roswell Park Bioanalytics, Metabolomics & Pharmacokinetics Core Facility, Center for Genetics and Pharmacology, Room L1-140, I 248613, [name], [name], [name].

For additional information regarding the handling of pharmacokinetic samples, please contact Roswell Park's Bioanalytics, Metabolomics & Pharmacokinetics Core Facility laboratory at [contact] (Tel) or [contact] (Fax). [name] ([contact]); [name] ([contact])

PK blood samples will be sent to procurement lab for processing and storage. After hours samples will be processed in Lab Medicine.

Network Site see Appendix H for specific instruction.

Note: All investigator or analyzing research laboratories housing research samples need to maintain current Temperature Logs and study-specific Sample Tracking and Shipping Logs. The Principal Investigator/Laboratory Manager must ensure that the stated lab(s) have a process in place to document the receipt/processing/storage/shipping of study-related samples/specimens. This is required for both observational and interventional clinical studies collecting clinical samples.

7.7.2 Sirolimus Levels

Pharmacokinetic analysis of sirolimus levels will not be done for patients participating in the exploratory cohort. Based on the completed trial (I 191511 “A Phase 1 Clinical Trial of mTOR Inhibition With Rapamycin for Enhancing Intranodal Dendritic Cell Vaccine Induced anti-Tumor Immunity In Patients with NY-ESO-1 Expressing Solid Tumors”), the 4 mg/day Sirolimus dose was safely used in combination with DEC205.

8 EFFICACY EVALUATIONS

8.1 Objective Tumor Response

All protocol-defined imaging studies must be performed at the investigative site or sponsor-approved facility using protocol-defined parameters. The same method of assessment and the same technique should be used to characterize each identified and reported lesion at baseline and during follow-up. RECIST 1.1 will be used to assess objective tumor response.

8.2 Target Lesions – PHASE 1

All measurable lesions up to a maximum of 2 lesions per organ and 5 lesions in total, representative of all involved organs, will be identified as target lesions and recorded and measured at baseline. Target lesions will be selected on the basis of their size. Lesions with the longest diameter (short axis for lymph nodes) and are ≥ 10 mm (CT and MRI), ≥ 15 mm lymph nodes, > 20 mm CXR and are for accurate repetitive measurements (either by imaging techniques or clinically) will be chosen. A sum of the longest diameter (short axis for lymph nodes) of all target lesions will be calculated and reported as the baseline sum diameters. This will be used as reference to further characterize the objective tumor response of the measurable dimension of the disease.

- **Complete Response (CR):** Disappearance of all target lesions. Any lymph nodes must have a reduction in short axis to < 10 mm. Changes in tumor measurements must be confirmed by repeat studies performed no less than 6 weeks after the criteria for response are first met.
- **Partial Response (PR):** At least a 30% decrease in the sum of diameters of target lesions, taking as reference the baseline sum diameters. Changes in tumor measurements must be confirmed by repeat studies performed no less than 6 weeks after the criteria for response are first met.
- **Progressive Disease (PD):** At least a 20% increase in the sum of diameters of target lesions, taking as references the smallest sum on study (this includes the baseline sum if that is the smallest on study). In addition to the relative increase of 20%, the sum must also demonstrate an absolute increase of at least 5 mm. The appearance of one or more new lesions is also considered progression.
- **Stable Disease (SD):** Neither sufficient shrinkage to qualify for PR nor sufficient increase to qualify for PD, taking as reference the smallest sum diameter while on study. Patients having a documented response with no confirmation of the response will be listed with stable disease.

8.3 Non-Target Lesions

All other small lesions (longest diameter < 10 mm or lymph nodes \geq 10 mm to < 15 mm short axis) and non-measurable lesions (i.e., leptomeningeal disease, ascites, pleural or pericardial effusion, inflammatory breast disease, lymphangitic involvement of skin or lung, blastic bone lesions, or abdominal masses / abdominal organomegaly identified by physical exam that is not measurable by imaging) should be identified as non-target lesions and indicated as present in the source documents at baseline. The general location will also be documented on the images drawing a regularly-shaped Region of Interest. Measurements of the non-target lesions will not be performed, but the presence or absence of each should be noted throughout follow-up and evaluation.

Those patients, who have no evidence of disease at the baseline, will be documented as no evidence of disease until progression of disease is documented per RECIST 1.1.

- **Complete Response:** Disappearance of all non-target lesions and normalization of tumor marker level, if applicable. All lymph nodes must be non-pathological in size (< 10 mm short axis).
- **Non-Complete Response/Non-Progressive Disease:** Persistence of 1 or more non-target lesion(s) and/or maintenance of tumor marker level above the upper limits of normal.
- **Progressive Disease:** Appearance of 1 or more new lesions or the unequivocal progression of existing non-target lesions. Although a clear progression of non-target lesions is exceptional, in such circumstances, the opinion of the treating physician should prevail and the progression status should be confirmed at a later time.
 - TUMOR RESPONSE ASSESSMENT BY IRRC – PHASE 2
- Tumor Response will be assessed by the Immune-related response criteria (irRC) as published by Wolchok et al. (68). Response is defined as irCR, irPR or irSD over a period of at least 4 weeks. Disease Control by irRC is defined as irSD or irPR or irCR.

PROGRESSION-FREE SURVIVAL (PFS)

Progression-free survival will be determined for each patient with time origin at the start of the treatment (day 1) until the first occurrence of confirmed progression by irRC or date of death if the patient dies from any causes before progression. Every effort will be made to follow patients for progression after they discontinue the study.

OVERALL SURVIVAL (OS)

Overall survival (OS) will be measured for each patient with time origin at the start of the treatment (day 1) until recorded date of death. Every effort will be made to follow patients for overall survival after they discontinue the study.

Antitumor response based on total measurable tumor burden:

Only index and measurable new lesions are taken into account when evaluating total measurable tumor burden. The longest diameter and longest perpendicular diameter should be recorded in millimeters (mm). At the baseline tumor assessment, the sum of the products of the two largest perpendicular diameters (SPD) of all index lesion ($\geq 10 \times 10$ mm; five lesions per organ, up to 10 visceral lesions and five cutaneous index lesions) is calculated. At each subsequent tumor assessment, the SPD of the index lesions and of new, measurable lesions ($\geq 5 \times 5$ mm; up to 5 new lesions per organ: 5 new cutaneous lesions and 10 visceral lesions) are added together to provide the total tumor burden.

Time-point response assessment:

Percentage changes in tumor burden per assessment time point describe the size and growth kinetics of both conventional and new, measurable lesions as they appear. At each tumor assessment, the response in index and new, measurable lesions is defined based on the change in tumor burden (after ruling out irPD). Decreases in tumor burden must be assessed relative to baseline measurements (i.e., the SPD of all index lesions at screening).

irCR

Disappearance of all lesions in two consecutive observations not less than 4 weeks apart.

irPR

$\geq 50\%$ decrease in tumor burden compared with baseline in two observations at least 4 weeks apart.

irSD

50% decrease in tumor burden compared with baseline cannot be established nor 25% increase compared with nadir.

irPD

At least 25% increase in tumor burden compared with nadir (at any single time point) in two consecutive observations at least 4 weeks apart.

Overall response assessment:

The overall response is derived from time-point response assessment (based on tumor burden) as follows:

Index and new

Non-index non-

New non-measurable

Overall

Measurable lesions (Tumor Burden)	measurable lesions	lesions	Response
100%	Absent	Absent	irCR
100%	Stable	Any	irPR
100%	Unequivocal Progression	Any	irPR
$\geq 50\%$	Absent/Stable	Any	irPR
$\geq 50\%$	Unequivocal Progression	Any	irPR
$<50\% \text{ TO } <25\%$	Absent/Stable	Any	irSD
$<50\% \text{ TO } <25\%$	Unequivocal Progression	Any	irSD
$\geq 25\%$	Any	Any	irPD

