2.2 Phase IIb Primary Objectives

- To determine the progression free survival (PFS) (primary endpoint) using standard irRC criteria.

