4 PATIENT SELECTION

4.1 Inclusion Criteria

To be included in this study, patients must meet the following criteria:

1. Eligible patients will be women with epithelial ovarian, fallopian tube, or primary peritoneal carcinoma after chemotherapy with no evidence of disease or minimal residual disease for primary or recurrent disease. This may or may not be measurable. These patients would normally enter a period of observation after standard management.
2. Any HLA type. (Historic HLA typing is permitted.)
3. Tumor expression of NY-ESO-1 or LAGE-1 by IHC and/or RTPCR.
4. Life expectancy > 6 months.
5. Hematology and biochemistry laboratory results within the limits normally expected for the patient population, without evidence of major organ failure. Have the following clinical laboratory values:
 - ANC \geq 1,000/ μ L
 - PLT \geq 100,000/ μ L
 - Hgb \geq 8 g/dL
 - Total bilirubin \leq 1.5 x ULN
 - Serum aspartate aminotransferase (SGOT/AST) or serum alanine aminotransferase (SGPT/ALT) \leq 3 x ULN
 - Serum creatinine \leq 2 x ULN
6. Have been informed of other treatment options.

7. Age \geq 18 years of age.
8. Patient or legal representative must understand the investigational nature of this study and sign an Independent Ethics Committee/Institutional Review Board approved written informed consent form prior to receiving any study related procedure.
9. Have an ECOG Performance Status of \leq 2. Refer to **Appendix A**.
10. The ability to swallow and retain oral medication.
11. Patients of child-bearing potential must agree to use acceptable contraceptive methods (e.g., double barrier) during treatment.
12. Patients may have received previous NY-ESO-1 vaccine therapy. Patients who received maintenance paclitaxel or bevacizumab are eligible for enrollment provided they have discontinued therapy (at least 4 weeks for prior taxane or prior bevacizumab) prior to randomization and recovered from toxicities to less than Grade 2.

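### The Phase IIb progression rule, as printed, does not work for patients who enrol without measurable disease, and a confirmed progression has no stated date

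*Combined protocol and SAP*

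**What the plan says.** - **Endpoint.** Section 2.2 sets the Phase IIb objective: "To determine the progression free survival (PFS) (primary endpoint) using standard irRC criteria". The PFS paragraph, under the Phase 2 irRC sub-heading in section 8.3, runs from day 1 "until the first occurrence of confirmed progression by irRC or date of death if the patient dies from any causes before progression".
- **irPD.** Section 8.3 defines it as "At least 25% increase in tumor burden compared with nadir (at any single time point) in two consecutive observations at least 4 weeks apart". On what enters the burden: "Only index and measurable new lesions are taken into account when evaluating total measurable tumor burden".
- **Population.** Section 4.1, item 1, admits patients with "no evidence of disease or minimal residual disease for primary or recurrent disease. This may or may not be measurable".
- **RECIST text nearby.** Before the Phase 2 sub-heading, section 8.3 says that patients with no evidence of disease at baseline "will be documented as no evidence of disease until progression of disease is documented per RECIST 1.1". It lists "non-measurable lesions (i.e., leptomeningeal disease, ascites, pleural or pericardial effusion" among non-target disease. For progression of non-target disease it adds that "the progression status should be confirmed at a later time". Section 8.2 is labelled Phase 1; sections 8.1, 8.3 and 8.4 have no phase in their headings. Section 8.4 gives its purpose as measuring time to progression, and in its Tables 5 and 6 any new lesion is progression at a single time point.
- **Confirmation and imaging.** Section 8.4 schedules a confirmatory assessment only after a partial or complete response. Section 6.7 lists progression as a reason to stop treatment. Table 3, footnote 4, leaves CT at early termination to discretion, and section 7.3 leaves imaging to standard of care.

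**The concern.** The trial enrols patients in remission, so some will start with nothing to measure. A progression rule built on percentage growth of measurable lesions has no starting value for them. RECIST wording in the same section would handle them, but the plan does not say that it applies to Phase IIb. Two analysts could read the same scans, follow the text faithfully, and reach different event counts. They could also reach different dates, because the plan does not say which of the two scans dates a confirmed progression.

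This affects the primary endpoint of an open-label trial with 25 patients per arm. If the rule is settled after PFS by arm is known, the choice is open to question.

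**Working it through.** **1. The two sets of rules applied to the same finding.**

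| Baseline | Finding | Printed irRC rule (8.3, Phase 2) | RECIST text (8.3, Tables 5 and 6) |
|---|---|---|---|
| No evidence of disease | New ascites | Burden stays at 0; new non-measurable lesions do not decide the outcome in the irRC table; no event | New lesion: progression |
| No evidence of disease | New 5 x 5 mm lesion | Burden goes from 0 to 25 mm²; the rise is 25/0, undefined; progression is the sensible reading but is not stated | New lesion: progression |
| Non-measurable residual disease | Unequivocal worsening | Burden stays at 0; not irPD | Progression (8.3 asks for later confirmation) |
| Index lesions present | Non-measurable worsening, burden up by less than 25% | irSD or irPR by the table | Progression |

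The first three rows are the defect. The fourth is a choice that the irRC table states openly, and it is not criticised here.

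**2. Dating.** The PFS paragraph refers to the first occurrence of confirmed progression but does not say which scan supplies the date. The only explicit date rule, in section 8.5, covers one FDG-PET situation. If the second scan comes 4 weeks later, the two readings differ by 28/30.4375 = 0.92 months. If progression is first seen at the 3-month follow-up and confirmed at the 6-month follow-up, they differ by 91/30.4375 = 2.99 months.

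**3. The plan's own figure.** Section 11.1.1 gives power of 0.70 for medians of 16 and 8 months. It states no alpha; I assume two-sided 0.05. By Schoenfeld's formula with all 50 patients having an event, power = Φ(√50 × ln 2 / 2 − 1.96) = Φ(2.451 − 1.960) = Φ(0.491) = 0.688. The stated figure is thus reproduced only when virtually every patient has a counted event. That shows why event counting matters. It does not measure a loss.

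**4. Scheduled scans, illustration only.** Assumptions: exponential PFS, no drop-out, every event a scan-detected progression, 25 per arm, median 8 months in 2a and 16 months in 2b. Cycle 4 Day 1 is day 84 (3 × 28). Last dose is day 113 in 2a (4 × 28 + 1) and day 195 in 2b (7 × 28 − 1). Scans follow at last dose + 30, + 91 and + 182 days.

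- Events first seen between scans s and t: 25 × (2^(−s/m) − 2^(−t/m)), with s, t and the median m in months.
- 2a, days 84/143/204/295: 5.32, 3.04, 2.65, 3.19.
- 2b, days 84/225/286/377: 2.82, 4.03, 1.51, 2.02.
- Total 24.6, of which 3.19 + 2.02 = 5.2 are first seen at the last scheduled scan, with no later scheduled scan to confirm them.
- With both medians 16 months: 4.3 of 19.0. With both 8 months: 5.7 of 30.7.
- With the 2b scan days in both arms: 2.528 + 2.021 = 4.549, about 4.5 of 26.8.
- Events by 60 months: 25 × (1 − 2^(−60/8)) + 25 × (1 − 2^(−60/16)) = 24.86 + 23.14 = 48.0. So 48.0 − 24.6 = 23.4 fall after the last scheduled scan and rest on standard-of-care imaging or death.

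These counts show that confirmation often depends on unscheduled imaging. They say nothing about how many relapses are non-measurable, which is the main defect.

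**The case against.** The best defence is that the plan has one PFS definition and it is irRC. The RECIST block begins at section 8.2, labelled Phase 1, runs on into section 8.3, and ends at the Phase 2 sub-heading. The sentence on patients with no evidence of disease lies inside that block, and Tables 5 and 6 use its vocabulary. This is a fair reading. A reader might infer that the plan flatly contradicts itself on the primary event; the documents do not prove that, because the conflict depends on missing phase labels. But if the RECIST text is Phase I only, the irRC rule stands alone in Phase IIb, and it has no workable rule at zero burden.

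Three further points have force:

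- **Later events can still count.** A reader might infer that a non-measurable relapse can never be an event. That goes too far. New lesions are measurable from 5 x 5 mm, section 8.3 asks that patients be followed for progression after leaving the study, and death always counts. Such a relapse may therefore be counted late.
- **Unconfirmed progression.** A reader might infer that no rule covers it. On the plain wording of the PFS paragraph it is a non-event, and that is a stated choice. Still, confirmation is scheduled only after response, and progression can end treatment, so some true progressions may go uncounted. The documents do not say how many.
- **The cited irRC publication may fill the gap.** It is cited as reference 68, while the list ends at 44. That is a citation fault and does not show that the publication lacks a rule. The plan as printed does not supply one.

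**Conclusion.** The point holds in this form: the printed irPD rule cannot be applied to patients who start with no measurable burden, a non-measurable relapse in them is not an event unless it later becomes measurable or they die, and the date of a confirmed progression is unstated. This should be fixed.

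The dating gap is about 0.9 to 3.0 months per affected event. The number of patients and relapses affected cannot be derived from the documents, which give neither the share enrolled without measurable disease nor the share of relapses that are non-measurable.

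Two inferences are not supported. One is that about a fifth of events are lost (5.2 of 24.6). That figure covers scheduled scans only, leaves out standard-of-care imaging, changes with the assumed scan days, and does not measure the defect. The other is a specific loss of power; reproducing 0.70 with nearly complete events shows sensitivity to event counting, not how many events would be missed.

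**What to change.** Before PFS by arm is seen:

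1. Label sections 8.1, 8.3, 8.4 and 8.5 by phase and reconcile them with section 2.2 and the PFS definition. Say whether symptomatic deterioration and tumor markers (8.4), and the effusion-cytology and FDG-PET rules (8.5), bear on Phase IIb PFS.
2. State that the existing RECIST 1.1 sentence in section 8.3 applies to Phase IIb PFS for patients with no evidence of disease. State the rule for non-measurable residual disease as well; the non-target progression rule in section 8.3 is the natural one. An unequivocal new lesion, measurable or not, is then an event.
3. Keep confirmed irRC for patients with index lesions. Date a confirmed progression at the first scan that meets the criterion.
4. Add two sensitivity analyses: RECIST 1.1 PFS in all patients, and PFS counting unconfirmed progression as an event at the first scan. The second leaves the plan's choice of confirmed events intact for the primary analysis.

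The cost is a protocol and SAP amendment, with no extra scans or patients. The drawbacks are that the criterion differs by baseline disease status and that some pseudo-progressions may count as events; the analyses in step 4 show how much either matters.
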